4. STUDY OBJECTIVE

4.1. Study Objective

The objective of this study is to assess the safety and to demonstrate efficacy of cryoablation in local tumor control for tumors ≤ 3.5 cm in patients with pulmonary metastatic disease.

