7.5. Month 1 – Follow-up

Patients will return 1 month (30 days $-7/+21$) post cryoablation procedure. In the event of multiple cryoablation procedure dates, the most recent procedure date will serve as the reference for determining the follow up visit window.

The following assessments will be completed:

- Quality of Life assessment (SF-12);
- Karnofsky Performance Scale;
- Safety assessment;
- Chest CT scan \pm contrast (contrast is preferred) to identify possible post-procedure adverse events. This 1 month imaging will serve as the new baseline for tumor response evaluation;
- Assessment of metastatic lung disease progression beyond the index tumor(s) and feasibility of treatment;
- Assessment of local tumor recurrence at the index tumor, including additional treatment and feasibility of treatment;
- Assessment of any systemic cancer treatment(s);
- Assessment of any local therapy for the index tumor(s).
- Current pertinent concomitant medication.

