7.8. Repeat Cryoablation Treatment(s) or Alternative Additional Treatment

Patients may receive additional cryoablation treatment(s) to the index tumor(s) initially subjected to cryoablation while participating in the study protocol. This additional cryoablation may be performed on the index tumor(s) provided that the additional treatment is performed with Galil Medical technology. In this situation, for each index lesion retreated, follow-up visits will restart per the study protocol and continue through the 24 month visit after the date of the repeat cryoablation treatment. When possible, if multiple tumors are present, all efforts should be made to align all follow up visits. For any index lesion not subjected to retreatment, the data collection continues per protocol.

- Baseline labs are recommended to be repeated prior to any repeat cryoablation procedure;
- It is recommended to discontinue anticoagulation as clinically indicated;

- SF-12 will not be collected prior to or after any repeat cryoablation of index tumor(s);
- Pertinent medications should be reviewed prior to and after any repeat cryoablation of index tumor(s);
- All other follow-up requirements are still applicable.

If other local treatment (e.g. radiofrequency ablation, microwave ablation, surgery, radiation) is used on the index tumor(s) initially treated, then the patient must be withdrawn from the study.

Data will be collected regarding any systemic cancer therapy the patients receive during the course of the study.

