7.9. Study Completion or Withdrawal

Patients may withdraw from this study at any time, with or without a reason, without prejudice to further treatment. Investigators should make every effort within the bounds of safety and patient choice to have each patient complete the study. If a patient does not return for a scheduled visit, every effort should be made to contact the patient. In any circumstance, every effort should be made to document patient outcome, if possible. The investigator should inquire about the reason for withdrawal; request the patient return for a final visit, if applicable, and follow-up with the patient regarding any unresolved adverse events. If possible, the reason(s) for withdrawal (if given) will be recorded.

If the patient withdraws from the study and also withdraws consent for disclosure of future information, no further evaluations should be performed and no additional data should be collected. The sponsor may retain and continue to use any data collected before such withdrawal of consent.

Patients who request Early Termination from the study will be asked to return if physically capable for a final visit to complete the following assessments.

- Karnofsky Performance Scale;
- Chest CT scan, \pm contrast (contrast is preferred);
- Safety assessment;
- Assessment of metastatic lung disease progression, including additional treatment;
- Assessment of any new cancer treatment(s).

In the event the patient enters hospice or another similar care program, early termination should be documented. Information taken from the medical record is sufficient to document this reason for early termination in the event this communication is not provided by the patient.

Patients may be considered "lost to follow-up" after 3 unsuccessful attempts to contact the patient with one contact being a registered letter to the last known address of the patient. Site should document all attempts to contact the patient in the source documents.

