7.10. Pertinent Concurrent Medications

Data will be collected regarding concurrent pertinent medication taken at the time of screening and through 30 days post procedure. In the event of multiple cryoablation procedures, the pertinent medications will be followed through 30 days of the last procedure. Any medication which could affect the outcomes of this study should be included. Examples of pertinent medication include any medication taken for the following indications:

- Treatment of cancerous tumors within the lung;
- Improve/affect lung function (including cough);

- Anticoagulation therapy;
- Antiplatelet therapy.

Medications recorded at screening which are prescribed for coagulopathy or bleeding disorders must appropriately wash out before the cryoablation procedure according to the investigator's standard of care. These medications include, but are not limited to, warfarin (e.g. Coumadin), clopidogrel (e.g. Plavix), Phenindione (e.g. Dindevan) and aspirin. Herbal supplements with blood thinning properties should also be washed out appropriately.

Supplemental treatment which, in the investigator's opinion, becomes necessary during the course of the study must not be denied to the patient. If this supplemental treatment is described as a therapy expressly not permitted or which may affect the primary efficacy outcome, the patient's participation in the study will need to be discontinued due to non-permitted concurrent therapy.

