For the formal primary endpoint hypothesis test, patients with missing 12-month tumor evaluations will be imputed using multiple imputation (SAS PROC MI using FCS logistic regression and including tumor status at prior visits), except in the following case where previous visit evidence can be used to impute 12-month status:

- Subjects with local tumor failure at 6-months will be considered a local tumor failure at 12-months post-index procedure.

Additional sensitivity analyses to be conducted:

- Worst case: all missing data are imputed to be failures
- Best case: all missing data are imputed to be successes
- Complete case: all missing data are treated as missing and not imputed

Subset Analyses

Analysis will be done on outcomes for subgroups including, but not limited to, gender and lesion size. Additional non-protocol defined subgroups include: number of needles used, number of lesions, primary cancer diagnosis, and lesion location.

Poolability Analyses

A poolability analysis among investigational centers and geographies (US/OUS) will be performed for the primary efficacy endpoint. This analysis will be performed on the ITT population.

Poolability of Sites

Combining of Small Sites

Sites contributing less than 5 subjects to the as treated analysis set will be considered “small sites” and ordered by the date of first enrollment in the as treated analysis set. Starting with the first “small site”, a pseudo-site will be created by adding subjects from successive “small sites”. If the number of subjects reaches or exceeds the size of the median enrollment of the “large sites”, then a second pseudo-site will be created. Additional pseudo-sites, if needed, would be created in the same manner.

Primary Endpoint by Site

Among sites and pseudo-sites, the proportions of subjects who achieve local tumor control at 12 months will be compared using logistic regression. If the resulting p-value is ≤ 0.05 , further exploratory analysis will attempt to identify covariates (baseline characteristics) that may explain differences among the sites. Otherwise, the data will be considered to be poolable across study sites.

Poolability of Geographies

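### Systemic cancer therapy is recorded from Month 1 but enters no pre-specified efficacy analysis or named imputation predictor, and Protocol 7.8 and 7.10 disagree on whether patients who receive it stay in the study

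*Protocol*

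**What the plan says.** The Protocol's objective (4.1) is "to demonstrate efficacy of cryoablation in local tumor control for tumors" up to 3.5 cm. The patients have Stage 4 disease (6.2.3) and there is no control arm. Exclusion 6.3.8 bars concurrent experimental studies that could affect the primary endpoint; standard systemic therapy is not excluded.

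On treatment during the study, Protocol 7.8 separates two cases. If another local treatment "is used on the index tumor(s) initially treated, then the patient must be withdrawn from the study". For systemic therapy it says only that "Data will be collected regarding any systemic cancer therapy the patients receive during the course of the study". Sections 7.5 to 7.7 list an assessment of systemic cancer treatment at Months 1, 3, 6, 12, 18 and 24, and 7.9 asks about new cancer treatment at early termination. Before Month 1 the source is the medication record in 7.10: "Data will be collected regarding concurrent pertinent medication taken at the time of screening and through 30 days post procedure". The first example given there is "Treatment of cancerous tumors within the lung".

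Section 7.10 ends with a different rule. Necessary supplemental treatment must not be denied, but if it may affect the primary efficacy outcome, participation is to be discontinued for non-permitted concurrent therapy.

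The SAP's primary analysis is a random effects logistic model for within-subject correlation, with no covariate named. The only named predictor in the multiple imputation is tumor status at earlier visits. The listed sensitivity analyses vary only the handling of missing data. The subgroups begin with gender and lesion size, and the SAP continues: "Additional non-protocol defined subgroups include: number of needles used, number of lesions, primary cancer diagnosis, and lesion location". Concomitant medications and prior treatments for lung metastases appear only among the descriptive summaries.

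**The concern.** Local failure (Protocol 8.7.4) is a growth of at least 20% from nadir in the summed diameters of the ablation zone. A drug active against the tumor can prevent or delay that growth. The Protocol accepts as much: it excludes experimental chemotherapy because it could affect the primary endpoint, and it collects medication that could affect the outcomes.

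With one arm tested against a fixed 84%, the comparison itself cannot separate the effect of ablation from that of background drugs. What could help is a pre-specified look at control by systemic therapy, and an imputation that knows who was treated. The SAP has neither, although the data will be in the database. A breakdown chosen after the result is known would carry less weight than one fixed beforehand.

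**Working it through.** **1. What happens to a treated patient under each section.**

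- If 7.8 is followed, the patient stays, the Month 12 scan is read, and any drug effect on the index tumor is part of the observed rate.
- If 7.10 is followed, and the therapy is judged able to affect the primary efficacy outcome, the patient is discontinued and the Month 12 reading is likely to be missing. Except after a 6-month failure, which the SAP carries forward, the value is imputed, with prior tumor status as the only named predictor. Departure is then tied to treatment, but treatment is not in the imputation model.

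Neither document says which section governs systemic therapy. Sites could differ, so both mechanisms could operate in one data set.

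**2. The plan's own figures.** Inputs from Protocol 10.1: N = 203 tumors, reject at 181 or more, P0 = 0.84, P1 = 0.91, one-sided exact binomial.

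- P(X ≥ 181 | 203, 0.84) = 0.0239, as stated.
- P(X ≥ 181 | 203, 0.91) = 0.8501, as stated.
- P(X ≥ 180 | 203, 0.84) = 0.0384, above 0.025, so 181 is the right cut-off.
- 203 / (1 − 0.10) = 225.6, rounded up to 226, as stated.

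**3. Illustration of scale, for patients who stay in.** The documents give neither the share of tumors in treated patients (f) nor the gain in control among them (d), so both are assumed. Tumors are taken as independent, as in the SAP's sample size section. Cryoablation alone is set at exactly 84%, the boundary of the null hypothesis, so that any rise is a rise in the chance of a success that cryoablation alone would not earn.

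Overall rate = 0.84 + f × d. Chance of meeting the goal = P(X ≥ 181 | 203, overall rate). The share of would-be failures that the drug must prevent is d / 0.16.

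| f | d (points) | Failures prevented | Overall rate | Chance of meeting the goal |
|---|---|---|---|---|
| 0 | – | – | 84.0% | 2.4% |
| 20% | 1.6 | 10% | 84.3% | 3.1% |
| 20% | 5 | 31% | 85.0% | 5.5% |
| 40% | 4 | 25% | 85.6% | 8.6% |
| 30% | 10 | 62.5% | 87.0% | 21% |
| 40% | 8 | 50% | 87.2% | 23.6% |
| 60% | 8 | 50% | 88.8% | 49.1% |

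The range, 3.1% to 49.1%, depends wholly on the assumed inputs. If cryoablation alone gave 80%, then 20% treated with 10% of failures prevented gives 0.80 + 0.2 × 0.1 × 0.20 = 80.4% and a chance of 0.06%. With 60% treated and 50% prevented the rate is 0.80 + 0.6 × 0.5 × 0.20 = 86% and the chance is 11.3%.

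**The case against.** The strongest objection is that neither the direction nor the size of any net bias is established. The 84% goal was set by clinicians from published series. The documents do not say whether those patients also had systemic therapy; if they did, the benchmark already contains some of the effect. Therapy begun after ablation may also follow progression, so treated patients could be the worse group. Both arguments stand, and they rule out any claim that the rate is inflated by a known amount.

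A second objection is that the SAP is not wholly silent. Its subgroup list is open-ended, primary cancer diagnosis is a partial proxy for drug treatment, and the per-protocol set can drop deviations likely to affect the outcome. These narrow the gap without closing it: none names systemic therapy, and an open-ended list leaves the choice until after the result is seen.

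Three stronger readings are tempting, and the documents do not support them:

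- That systemic therapy is plainly permitted, so its effect is simply credited to cryoablation. Section 7.10 points the other way, and under it the problem is missing data.
- That it is recorded at every visit. The item starts at Month 1. Week 1 lists only pertinent medication, and Table 1 has no row for systemic treatment.
- That background drugs could turn a probable failure into a probable success. Starting from 86% for cryoablation alone, a 10-point gain in half the patients lifts the rate to 91% and the chance of meeting the goal from 11% to 85%. But 86% already exceeds 84%, so this is extra power for a true conclusion, and it needs the drug to prevent 10/14 = 71% of would-be failures.

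**Conclusion.** The point holds as a gap in pre-specification together with an unreconciled conflict. Systemic therapy is foreseeable in these patients, is collected from Month 1, and bears on a size-based endpoint; no pre-specified efficacy analysis or named imputation predictor uses it. As written, the plan cannot show whether 12-month control depends on background drugs, and sections 7.8 and 7.10 leave open whether treated patients are observed or imputed.

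The size cannot be derived from the documents. At a cryoablation-alone rate of exactly 84%, the chance of meeting the goal moves from 2.4% to 5.5% (20% of tumors treated, 5-point gain) or 21% (30%, 10 points). These figures rest on independent tumors, the exact rule used for sample size rather than the final model-based Wald bound, no missing data, and a benchmark free of drug effect. If the reference series included systemic therapy, the concern is smaller. The change is worth making because it is cheap; nothing here shows that the primary test is invalid.

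**What to change.** 1. Reconcile Protocol 7.8 with 7.10, so that both say the same about a patient who receives systemic cancer therapy, and have the SAP state how the 12-month endpoint treats that patient. Which rule applies is for the sponsor and investigators to decide.
2. Add systemic therapy status, at screening and by visit up to Month 12, as a predictor in the multiple-imputation model. For patients who leave early, the termination visit records new cancer treatment, so status up to exit is available when that visit takes place.
3. Pre-specify, as a supportive analysis, 12-month tumor-level control by systemic anticancer therapy ongoing at screening (yes/no), with the same model and interval as the primary analysis. Status at screening precedes ablation and so cannot be a response to the result of the ablation.
4. Label any estimate restricted to patients with no systemic therapy through Month 12 as descriptive only. Remaining untreated may reflect not having progressed, so the trial's conclusion should not depend on it.

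The cost is a few SAP lines, one Protocol clarification and one extra table from data already collected. Intervals in the strata will be wide: with 20% of 203 tumors (about 41), the approximate 95% half-width is 1.96 × √(0.84 × 0.16 / 41) = 11 points at 84% control and 1.96 × √(0.91 × 0.09 / 41) = 9 points at 91%, before allowing for within-patient correlation. The primary test rule and the sample size do not change.

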7.9. Study Completion or Withdrawal

Patients may withdraw from this study at any time, with or without a reason, without prejudice to further treatment. Investigators should make every effort within the bounds of safety and patient choice to have each patient complete the study. If a patient does not return for a scheduled visit, every effort should be made to contact the patient. In any circumstance, every effort should be made to document patient outcome, if possible. The investigator should inquire about the reason for withdrawal; request the patient return for a final visit, if applicable, and follow-up with the patient regarding any unresolved adverse events. If possible, the reason(s) for withdrawal (if given) will be recorded.

If the patient withdraws from the study and also withdraws consent for disclosure of future information, no further evaluations should be performed and no additional data should be collected. The sponsor may retain and continue to use any data collected before such withdrawal of consent.

Patients who request Early Termination from the study will be asked to return if physically capable for a final visit to complete the following assessments.

- Karnofsky Performance Scale;
- Chest CT scan, \pm contrast (contrast is preferred);
- Safety assessment;
- Assessment of metastatic lung disease progression, including additional treatment;
- Assessment of any new cancer treatment(s).

In the event the patient enters hospice or another similar care program, early termination should be documented. Information taken from the medical record is sufficient to document this reason for early termination in the event this communication is not provided by the patient.

Patients may be considered "lost to follow-up" after 3 unsuccessful attempts to contact the patient with one contact being a registered letter to the last known address of the patient. Site should document all attempts to contact the patient in the source documents.

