7. STUDY PROCEDURES

The study schedule of events and the specific procedures performed at each visit are shown in Table 1, Schedule of Events. Each patient will undergo a total of 9 visits, including an initial/screening visit, the procedure visit, and 7 post-operative visits. More visits may be required when medically necessary.

Table 1: Schedule of Study Events

Procedures	Screening ^a	Procedure Date	W 1 ^c	M 1 ^e	M 3 ^{g,h,i}	M 6, 12, 18, 24 or W/D ^{g,h,i}
Informed Consent	X					
Inclusion/Exclusion	X					
Demographics	X					
Targeted Medical History	X					
Karnofsky Performance	X			X	X	X
Pertinent Medication	X		X	X		
Discontinue anticoagulation, as clinically indicated	X	X				
Imaging Scan	X ^f		X ^d	X ^f	X ^f	X ^f
Record index tumor characteristics	X					
Cryoablation procedure		X ^b				
Labs	X					
Quality of Life (SF-12)	X			X	X	
Safety Assessment		X	X	X	X	X

^a All screening visit requirements should be within 8 weeks of the initial cryoablation procedure. Any items (e.g., imaging or lab assessment) previously conducted as routine standard of care prior to the signed informed consent may be used to satisfy the screening requirements provided they are completed within 8 weeks of the initial cryoablation procedure.

^b If multiple tumors are planned for study inclusion, treatment of all study index tumors should be completed within an 8 week window.

^c The week 1 follow up visit may take place prior to discharge from the hospital or within 1 week (7 days) of the cryoablation procedure.

^d Week 1 imaging may be a chest CT ± contrast or chest X-Ray

^e Month 1 visit window 30 days -7/+21 days

^f Chest CT scan ± contrast (contrast is preferred)

^g Months 3, 6, 12, 18 and 24 visit window +/- 30 days

^h In the event of multiple cryoablation procedure dates, the most recent procedure date will serve as the reference for determining the follow up visit window.

ⁱ While return visits are preferred to be conducted in the clinic setting, in the event the patient is not able to return due to distance or illness, follow up assessments (i.e. all assessments with the exception of imaging) may be conducted via telephone or tele-video (e.g. Skype). Tele-video should only be considered if the patient has the knowledge and access to such technology.

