7.7. Months 6, 12, 18 and 24 – Follow-up

Patients will return 6, 12, 18, and 24 months (+/-30 days) post cryoablation procedure. In the event of multiple cryoablation procedure dates, the most recent procedure date will serve as the reference for determining the follow up visit window.

The following assessments will be completed:

- Karnofsky Performance Scale;
- Chest CT scan \pm contrast (contrast is preferred);
- Safety assessment;
- Assessment of metastatic lung disease progression beyond the index tumor and feasibility of treatment;
- Assessment of local tumor recurrence at the index tumor, including additional treatment and feasibility of treatment;
- Assessment of any systemic cancer treatment(s);
- Assessment of any local therapy for the index tumor(s).

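### Protocol 7.9's itemised exit visit is worded for patients who ask to leave and omits index-tumor recurrence, so a local failure first seen between visits can go unrecorded and bias 12-month control upward

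*Protocol*

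**What the plan says.** **Scheduled visits.** Protocol 7.7 lists, among other items, "Assessment of local tumor recurrence at the index tumor, including additional treatment and feasibility of treatment". It has separate items for lung progression beyond the index tumor and for local therapy to the index tumor.

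**Table 1.** Withdrawal shares a column with the later visits ("M 6, 12, 18, 24 or W/D"). KPS, imaging and safety are marked there, with no limit to exits the patient asks for. Table 1 has no row for recurrence or feasibility at any visit, so those items come only from 7.5 to 7.7.

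**Exit visit.** The itemised list in 7.9 is introduced by "Patients who request Early Termination from the study will be asked to return if physically capable for a final visit". It contains KPS, chest CT, safety, new cancer treatment, and "Assessment of metastatic lung disease progression, including additional treatment". It has no line for recurrence at the index tumor and none for feasibility of treatment.

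**Other withdrawals.** The opening paragraph of 7.9 tells the investigator to "request the patient return for a final visit, if applicable, and follow-up with the patient regarding any unresolved adverse events", and adds: "In any circumstance, every effort should be made to document patient outcome, if possible".

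**Withdrawal by rule.** Under 7.8, if another local treatment "is used on the index tumor(s) initially treated, then the patient must be withdrawn from the study". Section 7.10 discontinues patients who need therapy that is not permitted or may affect the primary outcome.

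**Analysis.** Protocol 10.5.3 takes as denominator the tumors evaluated at 12 months. The SAP (Handling of Missing Data) multiply imputes missing 12-month status from tumor status at prior visits. Its one exception is that a local failure at month 6 counts as a failure at month 12. Worst-case, best-case and complete-case analyses are sensitivity analyses.

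**The concern.** Patients whose index tumor has received surgery, radiation or another ablation are likely to include a disproportionate share of those in whom cryoablation did not hold. They request nothing, so the itemised exit visit is not addressed to them, and what remains is conditional. A CT prompted by the withdrawal comes after the other treatment and may show its effect. Read literally, 8.7.1 scores disappearance of the zone as complete response, so a CT after surgery could even look like a success.

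If the failure was first seen between scheduled visits and no per-tumor status was entered, the last recorded status is control. The imputation model learns from tumors that stayed under observation and will mostly impute control for such a tumor. Under the protocol's denominator the tumor disappears instead. Both routes push the estimated rate upward, in a single-arm trial judged against a fixed goal.

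**Working it through.** **1. The plan's own figures.** Inputs from protocol 10.1 and the SAP's Sample Size Justification: P0 = 0.84, P1 = 0.91, N = 203, reject if at least 181 tumors are controlled.
- Exact binomial: P(X ≥ 181 | 203, 0.84) = 0.0239 and P(X ≥ 181 | 203, 0.91) = 0.8501. Both match the plan.
- Attrition: 203 / 0.90 = 225.6, rounded up to 226. This also matches.

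**2. The lists side by side.**

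| Item | 7.7 (months 6–24) | 7.9 exit list | General paragraph of 7.9 |
|---|---|---|---|
| Applies to | all patients | those who request termination | withdrawals generally, if applicable |
| Chest CT | yes | yes | not named |
| Recurrence at index tumor | yes | not named | not named |
| Feasibility of treatment | yes | no | no |
| Local therapy to index tumor | yes | only within new cancer treatment | no |

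**3. Which failures are exposed.**
- First seen at a scheduled visit: recorded there under 7.5 to 7.7. A month-6 failure is also carried forward. A failure at month 1 or 3 only enters the imputation model as prior status.
- First seen between scheduled visits and followed by other local treatment before the next one: the patient is withdrawn under 7.8, and no text requires a per-tumor status dated before that treatment.
- First seen between months 6 and 12: even if recorded at exit, no SAP rule carries it forward.

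**4. Effect of one such tumor on the estimate.** If a true failure is imputed as controlled with probability q, the raw rate rises by about q/N. With q = 0.91 (an assumption, set at the design alternative) and N = 226, that is 0.91/226 = 0.0040, or 0.4 percentage points per tumor. The planned difference is 7 points.

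**5. Effect near the decision boundary** (independent tumors, exact one-sided 97.5% lower bound, evaluated-tumor denominator, no imputation).
- 181/203 = 0.8916, lower bound 0.8405: goal met.
- Add one failure that had been left out: 181/204 = 0.8873, lower bound 0.8356: goal not met.

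**6. Range over an unknown share.** Let f be the share of all true failures that leave unrecorded. The documents give no value for f. At a true rate of 0.84 in 226 tumors, the rate among evaluated tumors is 0.84 / [0.84 + 0.16(1 − f)], and 226 × 0.16 × f tumors are lost.

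| f (assumed) | Tumors lost | Evaluated rate | Chance of passing |
|---|---|---|---|
| 0 | 0 | 0.840 | 0.023 |
| 10% | 3.6 | 0.854 | 0.062 |
| 25% | 9.0 | 0.875 | 0.262 |
| 50% | 18.1 | 0.913 | 0.873 |

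Steps 5 and 6 show direction and sensitivity only. The SAP's formal test is a random-effects logistic model with multiple imputation, and it was not simulated.

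**The case against.** The best defence is that much of the needed data is already scheduled. Table 1 marks imaging at any withdrawal. Section 8.7 has each ablation zone measured in three axes at each time point, and 16.2 adds central review. The progression item in 7.9 omits the limit to disease beyond the index tumor, and 10.5.5 describes lung tumor progression as including local failure of the index tumor. Failures found at scheduled visits are entered before any other treatment is given. The worst-case analysis counts every missing tumor as a failure.

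All of this stands and narrows the point. It does not close the gap. A scheduled CT that follows other local treatment does not measure cryoablation control, the general paragraph of 7.9 is conditional, and the worst-case analysis is not the formal test.

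Three stronger readings are tempting and are not supported:
- A reader might infer that the protocol removes patients for failing. It does not. The triggers are other local treatment and non-permitted therapy, and 7.8 lets a failing tumor be treated again with cryoablation on study.
- A reader might infer that no site assessment of the index tumor is made at exit. Imaging is scheduled at exit, and the progression item can be read to cover the index tumor.
- A reader might assume that 25–50% of failures receive other local treatment and infer that 5–18 lost tumors use up 23–82% of the permitted failures. The documents give no such share, and not every such tumor would go unrecorded. That sum also sets failures among 226 tumors against the allowance for 203 (203 − 181 = 22). The same exact rule at 226 needs 201 controlled and so allows 25.

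**Conclusion.** The point holds in a limited form. The exit provisions in 7.9 do not match 7.7, the itemised list is not worded for patients withdrawn by rule, and the SAP carries forward only a month-6 failure. A local failure first seen between scheduled visits and then given other local treatment can therefore miss the primary analysis as a failure, and the resulting bias is upward.

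The size is unknown. It depends on how many failures surface off schedule and on how consistently sites record status at exit, and the documents inform neither. Each affected tumor moves the raw rate by roughly 0.4 points under the stated assumption, and near the boundary one tumor can decide the result. That is sufficient reason to close the gap, but it is no evidence that the result will be wrong.

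The missing feasibility items affect only the two time-to-untreatable outcomes, which carry no hypothesis test. Feasibility is asked at every scheduled visit from month 1, so those outcomes lose information at exit without losing all their events. The design figures are not in dispute.

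**What to change.** 1. **Protocol 7.9.** Replace the exit list with the 7.7 list so that 7.7, 7.9 and Table 1 agree, and apply it to every discontinuation, whether by request or by rule. The withdrawal rules in 7.8 and 7.10 need no change for this purpose.
2. **eCRF.** For each index tumor given other local treatment, enter a dated local-control status read from the last available chest CT before that treatment. No new scan is needed.
3. **SAP, Handling of Missing Data.** Carry a local failure recorded at any time before month 12, including at exit, forward as a 12-month failure. Word the rule per tumor, to match the endpoint; the present rule speaks of subjects. Without this step, a failure recorded at exit between months 6 and 12 would still be imputed.

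The cost is amended wording, a few eCRF fields, and possibly a slightly lower reported control rate. Where no CT precedes the other treatment closely, the status will remain uncertain and should be reported as such.
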